Approach The advent of next generation DNA sequencing has revolutionized efforts to characterize the endogenous microbiome. In fact, these genomic-based technologies have revealed many new bacterial species that were missed using microbiologic and serologic approaches. The endogenous microbiota plays a critically important role in generating an efficacious immune system and a healthy functioning gut. Of relevance to this proposal, the microbiome also regulates susceptibility to obesity and diabetes. An oral medication, like ACA, will likely target the gut microbiome. Thus, subjects will self-collect feces in sterile containers and deliver it to the clinic at their regular visits. DNA isolation will be performed by the Genomics Core facility on a fee-for-service basis and the samples will be delivered to the Sequencing Core Facility for analysis. The bacterial rDNA in each fecal sample will be amplified using primers from conserved regions of the 16S ribosomal RNA genes. Amplified DNAs are then used to generate a library which is subsequently subjected to deep (next gen) sequencing.

Expected Results For humans, there have been many reports documenting the bacterial species that dominate in older vs. young individuals (24). Given the ages of our subjects, we would expect to see a profile more similar to the “old” profile. It would be most exciting if ACA were to alter the microbiome, making it more “youthful”.

Sub-study D Rapamycin Alone – Cardiovascular Effects

For Aims D-1, D-2, D-3, and D-4:

Intervention with RAPA will begin at the end of Visit 2 once all screening and baseline measurements have been collected. Subjects will self-administer RAPA once daily for a period of 8 weeks (56 doses) and there will be no placebo group in this Sub-study. We will screen 12 MALE subjects to complete 6. No females will be enrolled in this pilot substudy.

Clinical assessment: See also Sub-study A (except without OGTT). In substudies A, B and C, no detrimental diabetogenic effects of RAPA were found, i.e. OGTT, FBS, HbA1c were unaltered by RAPA.

If subjects have previously undergone all or part of screening labs/tests within the past 4 months, the data may be accepted for eligibility determination without screening labs or procedures having to be repeated.

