Approach. PWV will be measured before, during, and at the end of RAPA treatment as per Table 2. Measurement of aortic PWV is the simplest way to assess arterial compliance non-invasively in humans and reflects the ability of the arterial system to cope with systolic ejection volume. It also implies that the compliant arterial system's major function is to relay cardiac contraction during diastole. Indeed, cardiac contraction lasts only one third of a cardiac cycle of the time. Due to the distension of the compliant large arteries during systole, after the end of cardiac contraction, the compliant large arteries return to their initial dimension and thereby help maintain blood flow. This phenomenon is of key physiological importance as diastolic flow in arteries may represent more than half of cardiac output. Large artery compliance represents the dynamic force opposing ejection (also called impedance): if high, it helps in ejection, the lower the compliance, diastolic facilitation of ejection is lessened. Many methods have been proposed to quantify this phenomenon. The simplest non-invasive approach to measure arterial compliance is PWV, i.e., the transit time measurement of the pulse wave from the aortic valve to the terminus of the aorta (1). We will use the SphygmoCor system, which has been used in successful large clinical trials and population surveys. This device uses a large band piezoelectric probe and allows the arterial pulse recording in succession (carotid then femoral), both signals being synchronized with the same time basis (ECG R wave) (1). We have such a device available and are experienced with its use in humans. To measure PWV, the subject will rest in supine position for at least 5-10 min to reach the physiological baseline conditions, the room will be maintained at a standardized temperature, and the blood pressure will be

accurately measured within minutes from the PWV recording times. Serial longitudinal measurements are performed as summarized in Table 2. All PWVs will be done in fasting condition. Overall, the reproducibility of PWV measurements is good (CV in the range of 8-12%) (1).

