Expected Results-There are many reports documenting that the PWV is greater in older vs. young humans (1). Given the ages of our subjects, we expect to see a pattern of initially high PWV before RAPA treatment that would be reduced with RAPA. In the placebo group, we expect that their initially high PWV will be unaltered or increase during the study.

Aim D-2. Test whether RAPA treatment improves endothelial function in elderly subjects.

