****Depending on availability of subjects, shared lab equipment, and personnel resources, the vascular function assessments for baseline measurements of PWV and or LDF may be scheduled and performed at Visit 1 OR Visit 2 (see Table 2). This allows flexibility for the subject and facilitates protocol compliance for the research team.**

MRI Studies of Cardiac function and Cerebral Blood flow

Aim D-3. Examine whether mTOR inhibition improves diastolic function and increases cerebral blood flow in humans. We will explore whether mTOR inhibition with RAPA improves cardiac diastolic function and cerebral blood flow (CBF). Diastolic function and CBF will be measured by MRI **pre- and post-treatment with RAPA at Visits 2 and 4.**

Expected Results-There are reports that the cardiac function and CBF are improved in animal models by RAPA treatment {Chiao, 2016 #2623;Urfer, 2017 #2617}. Given the ages of our subjects, we expect to see a pattern of initially impaired diastolic function and CBF before RAPA treatment that would be improved with RAPA.

Aim D-4. Examine whether mTOR inhibition increases physical activity in humans.

Expected Results-RAPA treatment increases physical activity in animal models. {Miller, 2011 #1350;Urfer, 2017 #2617} . We anticipate that similar activity increases will be found in humans with RAPA administration.

Pilot data will be collected on at least 6 subjects to analyze whether treatment with RAPA increases physical activity. Using a Garmin Vivofit3 Activity Monitor [Garmin, Inc.] provided by the study to each participant. we will examine whether RAPA effects overall activity by measuring time, distance, step count, calories burned, total hours of sleep, periods of movement, and periods of restful sleep. Subjects will wear activity monitors continuously for approximately 2 weeks from consent to baseline visit at which we will download pre-intervention activity levels. Subjects continue wearing bracelet-style activity monitors throughout the study duration and upon returning to the clinic (4 weeks and 8 weeks of RAPA treatment), provide data downloads at each of the Visits 3 and 4. Participants will keep the activity

tracking devices after the study is complete as a thank-you for their participation {O'Brien, 2015 #2716;Schrack, 2016 #2715;Šimůnek, 2016 #2714}.

Data Analysis Plan:

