GDS (Geriatr Depression Scale)*			X	X		X	X	X	X		X
CLOX Assessment (cognitive assessment)*		X		X							
PET/MRI								0	0		0

Notes: X=scheduled procedure; O=optional procedure (if funding found and subject consents) *May be done over Visit 0 and Visit 1; #=procedure performed if > 2 weeks from prior measure at V1

Table 2. VISIT SCHEDULE: Sub-study D. Rapamycin Alone – Cardiovascular Effects

VISIT NUMBER	V1	V2	FU1	V3	FU2	V4
Visit goal	Consent/ screen (fasting)	Pre-drug (not fasting)	Phone follow up*	4 wks RAPA	Phone follow up*	8 wks RAPA
Week number		0	1	4		8
PROCEDURES	2-2.5h	3-3.5		2.5-3		4
Consent form and CLOX>10	✓					
SAFETY/AEs/METABOLIC						
Physical exam	✓	✓		✓		✓
ECG	✓					✓
Self reported Adverse Events (AEs)	✓	✓	✓	✓	✓	✓
CBC (blood cell counts)	✓			✓		✓
Fasting blood sugar/CMP	✓			✓		✓
Fasting lipids	✓					✓
HbA1c	✓					✓
Urinalysis	✓					✓
IMMUNE FUNCTION						
Serum for cytokine profiles	✓			✓		✓
Flow cytometry: T cell subsets	✓			✓		✓
T cell activation potential	✓			✓		✓
RAPAMYCIN LEVEL						✓
Meal/snack	✓					✓
COGNITIVE FUNCTION						
Geriatric depression scale		✓				✓
EXIT, SLUMS, TAPS		✓				✓
VR-36 QOL		✓				✓
PHYSICAL FUNCTION						
Hand grip and 40 foot walk		✓		✓		✓
Garmin VivoFit3 Activity Monitor	DISPENSE	BRING*		BRING*		BRING*
DISPENSE STUDY MED		✓		✓		
VASCULAR FUNCTION						
Aortic Pulse Wave Velocity (PWV)	✓**	✓**		✓		✓
Arteriolar Endothelial Function (LDF)	✓**	✓**		✓		✓
CARDIAC/CEREBRAL BLOOD FLOW FUNCTION						
MRI		✓				✓
Schedule MRI - Date						

*Telephone follow up of subjects to assess tolerability and or adverse reactions to RAPA will be conducted at least once between V2 and V3. If tolerating well after 1-2 weeks of RAPA treatment without side effects, no further calls may be necessary. If side effects are reported at any time during RAPA administration, the investigator may choose to modify dosing, if appropriate, and follow by phone on a weekly basis until resolved.

BRING* – At Visits 2, 3 and 4, subjects will bring their Garmin VivoFit3 Activity Monitor so that activity data can be downloaded to a protected server with adequate storage and backup.

**Depending on availability of subjects, shared lab equipment and personnel resources, the vascular function assessments for baseline measurements may be scheduled and performed at Visit 1 OR Visit 2. This allows flexibility and promotes protocol compliance.

Item 7

Risks Section. Risks are described in detail in the Step 2-Institutional Form.

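### Aim D-1 requires fasting pulse wave velocity, but Table 2 allows the baseline at a visit labelled not fasting

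*Combined protocol and SAP*

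**What the plan says.** The Approach under Item 6, Aim D-1 lists the conditions for PWV: supine rest, standardised room temperature, blood pressure taken within minutes, and fasting. The last is stated without exception: "All PWVs will be done in fasting condition". The same paragraph refers to Table 2 for the timing.

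Table 2 heads V1 as a fasting visit and V2 as "Pre-drug (not fasting". Its PWV row is ticked at V1 and V2 (both with the double-asterisk note), V3 and V4. The note says that "the vascular function assessments for baseline measurements may be scheduled and performed at Visit 1 OR Visit 2", depending on the availability of subjects, equipment and staff. The text after Aim D-2 says the same: "baseline measurements of PWV and or LDF may be scheduled and performed at Visit 1 OR Visit 2 (see Table 2". Neither attaches a fasting condition to V2.

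V3 and V4 carry no fasting label, but the row "Fasting blood sugar/CMP" is ticked at V1, V3 and V4 and not at V2. A meal or snack is ticked at V1 and V4, with no stated order relative to PWV.

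On design, the Sub-study D methods say that "there will be no placebo group in this Sub-study", and that 12 men will be screened to complete 6.

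**The concern.** A baseline PWV at V2 breaks either the fasting rule or the label on the visit, and nothing says which governs. A team following Aim D-1 would have the man fast for PWV at V2; a team following Table 2 would not. In the second case his baseline is not fasted while his on-drug values probably are.

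Aim D-1 rests on the change within each man. Without a concurrent control, any systematic difference in measurement conditions between baseline and follow-up is absorbed into the apparent drug effect. If a non-fasted baseline reads high, it creates an apparent fall in PWV; if it reads low, it hides a real one. Because logistics decide the visit, the mix of baselines is uncontrolled. The plan does not provide for recording prandial state, so a mismatch could not be identified afterwards. This pilot is meant to inform larger studies, so a distorted PWV change would carry into their planning.

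**Working it through.** **Text comparison**

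| Visit | Label in Table 2 | Fasting blood sugar ticked | PWV ticked |
|---|---|---|---|
| V1 | fasting | yes | yes (baseline option) |
| V2 | not fasting | no | yes (baseline option) |
| V3 | none | yes | yes |
| V4 | none | yes | yes |

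V2 is the only PWV visit with no fasting blood test, and the only one labelled not fasting.

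**Size of the possible distortion**

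The plan gives no sample size calculation and names no PWV test, so there is no stated figure to reproduce. What follows is an illustration.

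From the documents: n = 6 completers; PWV coefficient of variation (CV) 8–12% (Aim D-1 Approach).

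Assumed: the CV is independent error on each measurement and the only source of within-man variation; the shift *m* between non-fasted and fasted PWV is 3%, 5% or 10%; *k* of the 6 men have a non-fasted baseline and fasted follow-up; the test is a two-sided 5% paired t-test (critical value 2.571 on 5 degrees of freedom).

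1. SD of the paired change = √2 × CV: 11.3% (CV 8%) or 17.0% (CV 12%).
2. Standard error = SD/√6: 4.62% or 6.93%.
3. 95% half-width = 2.571 × SE: 11.9 or 17.8 points.
4. Bias in the mean change = (k/6) × m. For k = 3: 1.5, 2.5 or 5.0 points. For k = 6: 3, 5 or 10 points.
5. Chance of a significant change in the direction of the shift when there is no drug effect (nominal 2.5%), by simulation of 2,000,000 trials; k = 6 agrees with the non-central t distribution. In each cell the lower value is for CV 12% and the higher for CV 8%:

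| k | m = 3% | m = 5% | m = 10% |
|---|---|---|---|
| 1 | 2.8–3.0% | 3.1–3.3% | 3.6–4.0% |
| 3 | 3.7–4.4% | 4.6–6.0% | 7.5–10.6% |
| 6 | 5.5–7.7% | 8.6–14.2% | 21.7–41.8% |

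6. Masking: assume a true 10% reduction and a 5% shift in the opposite direction. With k = 3, power falls from 42% to 25% (CV 8%) or from 22% to 14% (CV 12%). With k = 6 it falls to 14% or 9%.
7. Added variance from mixing baselines, for k = 3 and m = 5%: sample variance of the shift = (6/5) × 0.5 × 0.5 × 5² = 7.5. The SD of change rises from 11.3 to √(128 + 7.5) = 11.6, or from 17.0 to √(288 + 7.5) = 17.2, which is negligible.

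**The case against.** The texts can be read together. The fasting rule is universal and specific to PWV, whereas the V2 label describes the visit as a whole, at which no fasting blood is drawn. The option to use V2 is permissive and covers laser-Doppler flowmetry (LDF) too, so a careful team could do PWV at V1 and LDF at V2, or ask the man to fast. On that reading a non-fasted baseline arises only if the specific rule is overlooked. The meal at V1 and V4 most naturally follows the fasting procedures.

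The numbers also rest on a shift the documents do not give, and a pilot with no named PWV test makes no formal decision that a false positive would corrupt. Counting both directions, total error stays at 5.0% for k = 1 at every assumed shift. For k = 3 it is only 5.3–5.7% (3% shift) or 5.8–6.7% (5% shift).

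Much of this limits the weight of the point. The shift is hypothetical, the fasted state at V3 and V4 is an inference, and the likely distortion is small beside the imprecision of six men. It does not remove the conflict: neither note asks for a fast at V2, and the label there says the opposite. The harmonious reading needs an instruction the plan does not contain. Fasting is the plan's own measurement standard, so no outside evidence on meals and PWV is needed to show that the schedule permits a departure from it.

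**Conclusion.** The concern holds. The current text both requires fasting for every PWV and allows the baseline at a visit labelled not fasting, in an uncontrolled comparison of about 6 men. Confidence in the textual conflict is high. Its numerical consequence cannot be derived from the documents, because the shift, its sign and the number of men affected are all unknown. Under the stated assumptions the effect is modest for a 3–5% shift in up to half the men, and substantial only if most baselines are not fasted or the shift approaches 10%. It should be corrected because the remedy costs little and, without a control group, the analysis cannot undo the mismatch.

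**What to change.** Reconcile the Aim D-1 Approach, the flexibility note after Aim D-2, and Table 2 with its note, so that baseline and follow-up PWV share the same prandial state:

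- Either take baseline PWV at V1, or state that men fast for PWV when it is done at V2.
- State in Table 2 that PWV at V3 and V4 is fasting, and that PWV precedes the meal or snack at V1 and V4.
- Apply the same condition to the general allowance under Overall Experimental Design for the principal investigator to move collections to an adjacent visit.
- Record prandial state at each PWV, so that any mismatch can be listed or left out in a sensitivity analysis. With six men such an analysis will say little, so preventing the mismatch matters more.

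LDF is outside the fasting rule and may stay at either visit, though using the same state throughout is advisable for consistency.

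The cost is text edits and one recorded field, with less scheduling freedom. PWV at V1 lengthens a 2–2.5 hour screening visit, is spent on men not yet found eligible, and falls about two weeks before dosing (Aim D-4 gives "approximately 2 weeks from consent to baseline visit", and treatment starts at the end of V2). Fasting at V2 adds a fast before a 3–3.5 hour visit for which no meal or snack is ticked.

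A separate clerical correction: delete the sentence in the Aim D-1 Expected Results reading "In the placebo group, we expect that their initially high PWV will be unaltered or increase during the study", since Sub-study D has no such group.

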Approach. It is well known that microvascular endothelial dysfunction precedes dysfunction in conduit arteries and is predominantly due to reduced NO bioavailability in both aging and disease states. Choi, et al (2), have developed microvascular function test that reflects primarily NO-dependent vascular function and is thus of significant clinical utility. This test uses rapid local heating of forearm skin from 34°C to 39°C to produce a hyperemic vasodilation (an increase in cutaneous vascular conductance (CVC=LDF/MAP)) that is 80% dependent on NO. This is the most robust test of NO-dependent dilation that can be performed non-invasively in humans, as the multifold increase in conductance from 34°C to 39°C is almost entirely effected by NO. Due to the noninvasiveness and ease of performing the test, we will use rapid local heating to 39°C to assess NO-dependent dilation and thus microvascular function. Rapid local heating to 39°C elicits a plateau which reaches 50% of maximal CVC as effected by local warming to 42°C, which allows for assessment of interventions that may alter maximal vasodilatory mechanisms that are NO-independent. Upon arrival in the laboratory, subjects will be placed in a semi-supine position in a dialysis chair and be instrumented on their right forearm for laser-Doppler flowmetry measurements of skin blood flow (SkBF) with a LDF probe equipped with a local heating unit and thermocouple. A Finapres cuff placed on one finger for blood pressure measurements (MAP). Local skin temperature (Tloc) at the LDF site will be held at 34°C for approximately 5-10 minutes to establish a stable baseline measurement. Tloc will be then increased at a rate of 0.1°C/sec to 39°C and then held constant. After LDF has reached a stable plateau (30–40 min) at Tloc=39°C, Tloc will be raised to 42°C for about 30 min to maximally vasodilate the skin (9, 15, 17). For data analysis, CVC will be calculated. Averages of maximal absolute values of CVC (in mV) with Tloc=34, 39, and 42°C will be calculated and compared both within and between subjects by repeated measures ANOVA. All of the needed equipment is available in [name] lab.

Expected Results. It is well known that NO-dependent vasodilation is reduced in older vs. young individuals (5, 6). We expect that CVC responses to skin warming to 39°C will increase both during and after RAPA when compared to pre-RAPA responses.

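### Aim D-2 gives CVC a unit that does not fit its definition, and does not say how the 39°C response will be related to the same session's 42°C maximum

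*Combined protocol and SAP*

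**What the plan says.** All of this is in the Combined protocol and SAP, Item 6, Sub-study D, Aim D-2, unless another place is named.

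- **Definition.** The Approach text introduces "cutaneous vascular conductance (CVC=LDF/MAP", that is, flow signal per unit of pressure. MAP is recorded with a finger cuff in the same session, and the text states "For data analysis, CVC will be calculated".
- **Role of the 42°C step.** Heating to 39°C is said to give a plateau at 50% of the maximum reached at 42°C, "which allows for assessment of interventions that may alter maximal vasodilatory mechanisms that are NO-independent".
- **Analysis.** The quantity is given as "Averages of maximal absolute values of CVC (in mV", taken at each of the three temperatures (34, 39 and 42°C). The method is stated only as values "compared both within and between subjects by repeated measures ANOVA". The factors are not named, and neither a ratio nor a contrast is given.
- **Expected result.** A higher CVC response to warming to 39°C, during and after rapamycin, compared with before. The 42°C value is not mentioned here.
- **Design.** Under the Sub-study D heading of Item 6 there is no placebo group, and 12 men are to be screened so that 6 complete. Table 2 places the LDF test at baseline (Visit 1 or Visit 2), week 4 and week 8.

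**The concern.** Two things are left open.

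First, a flow signal divided by a pressure cannot have mV as its unit. An analyst who reads the sentence literally would use the raw flow signal; one who follows the definition would use conductance. The two can give different answers if blood pressure changes between visits.

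Second, the aim is about NO-dependent endothelial function, and the protocol itself says the 42°C reading is there to pick up changes that do not depend on NO. The stated analysis treats the 42°C value as one more absolute level and never sets the 39°C response against it. A shift that raises CVC at every temperature would satisfy the expected result without any change specific to the 39°C response.

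Such shifts are plausible here. The probe site is given only as the right forearm. The baseline test may fall at Visit 1, which Table 2 marks as fasting, or at Visit 2, which it marks as not fasting. No control arm would absorb changes between sessions.

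**Working it through.** The plan gives no sample size, alpha, power or variance for Aim D-2, so there is no stated figure to reproduce. The check is a unit check followed by arithmetic on the protocol's own 50% figure. The sizes of change are assumptions.

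**1. Unit.** CVC = LDF/MAP. If LDF is in mV and MAP in mmHg, CVC is in mV/mmHg. A value in mV is LDF before division.

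The choice would matter only if raw LDF were in fact analysed. Suppose MAP falls from 100 to 90 mmHg with LDF unchanged. CVC then changes by a factor of 100/90 = 1.11, a rise of 11%, while the mV value does not move. With LDF unchanged, a MAP change of −5%, +5% or +10% moves CVC by +5.3%, −4.8% or −9.1% (from 1/0.95, 1/1.05 and 1/1.10).

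**2. 39°C against 42°C.** Set the baseline 42°C maximum to 100, so the 39°C plateau is 50. Percent of maximum = 100 × CVC39/CVC42.

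| Case | CVC39 | CVC42 | Change in CVC39 | Change in CVC42 | Percent of maximum |
|---|---|---|---|---|---|
| Baseline | 50 | 100 | – | – | 50 |
| +20% at 39°C only | 60 | 100 | +20% | 0 | 60 |
| +20% at both | 60 | 120 | +20% | +20% | 50 |
| +10 units at both | 60 | 110 | +20% | +10% | 54.5 |

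With assumed rises of 10% and 30% at 39°C only, percent of maximum is 55 and 65; with the same rises at both temperatures it stays at 50. The absolute 39°C value is the same in all three changed rows of the table. The 42°C value tells them apart.

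**3. Reading the response as the rise from 34°C.** Let b be CVC at 34°C. The baseline rise is 50 − b. If every temperature scales by 1.2, the rise becomes 1.2 × (50 − b), again +20%. Subtracting the 34°C level removes a constant added at all temperatures, but not a proportional shift.

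**4. Scale of a temperature-by-visit contrast.** On absolute CVC, the 39°C change minus the 42°C change is 10 − 0 = +10 in the 39°C-only case and 10 − 20 = −10 under a uniform 20% shift. The uniform shift therefore does not give zero. On log CVC the uniform shift gives ln 1.2 − ln 1.2 = 0. A contrast equivalent to the ratio must be taken on the log scale.

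**5. Pressure within a session.** CVC39/CVC42 = (LDF39/LDF42) × (MAP42/MAP39). If MAP is the same at both steps, pressure cancels and the ratio does not depend on how the unit question is settled.

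**The case against.** The case on the other side is substantial, and most of it limits the point.

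- **A reader might infer that raw flow will be analysed.** The documents do not show this. The text gives the formula, records MAP and says CVC will be calculated; only the unit in parentheses points the other way. A slip is the natural explanation, and the MAP illustration is conditional on the less likely reading.
- **A reader might infer that the 42°C maximum is left out.** It is not. It is one of the three temperatures to be averaged and compared.
- **A reader might infer that the planned data cannot separate the two kinds of change.** They can. A uniform shift would show at 42°C and a 39°C-specific change would not. The protocol also states no rule by which a rise at 39°C alone would be declared a success. What is missing is a named comparison, not the information.
- **Percent of maximum is not clearly better as the only measure.** If rapamycin also raises the 42°C maximum, the denominator is affected by treatment, and a real gain at 39°C would be hidden: +20% at both temperatures stays at 50%. The Background to Sub-study D reports vessel-wall as well as NO-related effects in mice, so this is a fair worry. It stands, and it is why absolute values should not be demoted.
- **Repeated measures ANOVA still partitions variance between subjects.** True, but with one arm and no stated subgroup there is no between-subject factor that bears on the aim. The wording is loose; the analysis is not invalid.
- **This is an exploratory pilot, and the ratio can be computed at any time.** That lowers the severity. It does not remove the value of stating in advance how 39°C and 42°C will be read together.

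**Conclusion.** The point holds as a minor clarification. The unit conflicts with the definition in the same paragraph, so the analysed variable should be stated. The analysis names no quantity that relates 39°C to 42°C, although the protocol gives the 42°C step that very role. As written, the expected result could be met by a shift common to all temperatures, from probe site, session or maximal capacity, with no control arm to reveal it.

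An assumed 20% rise reads as +20% in absolute 39°C CVC whether or not the 42°C value rises with it, while percent of maximum is 60 in one case and 50 in the other. This rests on the protocol's 50% plateau and on shifts that are proportional. For a shift that adds a constant, the ratio is only partly protected (54.5% in the example).

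The documents do not support saying that the 42°C reading is discarded, that uncorrected flow will be analysed, or that the collected data could not answer the question.

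**What to change.** Change the Aim D-2 analysis text as follows:

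1. State the variable as CVC = LDF/MAP with its unit (mV/mmHg if LDF is in mV).
2. Prespecify 39°C CVC as a percent of the same session's 42°C CVC, or the equivalent temperature-by-visit contrast on log CVC. Compare it within subject across baseline, week 4 and week 8, with visit as the factor.
3. Report absolute CVC at 34, 39 and 42°C beside it, at equal standing, and say that the measures will be interpreted jointly. A rise at 39°C with a stable 42°C value and a higher ratio points to a 39°C-specific change. A rise at both with an unchanged ratio is compatible with a uniform shift or with a treatment effect on maximal dilation, and should be reported as unresolved.
4. Remove the between-subject comparison, or name the factor it refers to.

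The cost is a few lines of analysis text; no measurement or visit is added. The ratio also carries the noise of the 42°C reading and can hide a real 39°C gain if treatment raises the maximum, so it should not stand alone. The change does not make up for the missing control arm or the small number of men.
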